---

## Protocol Amendment Summary of Changes

### Protocol History

Version Number	Type	Version Date
1.0	Original Protocol	11 May 2017
1.1	Amendment specific for US	03 July 2017
2.0	Global Amendment	13 December 2017
2.1	Amendment specific for US	16 November 2017
3.0	Global Amendment	12 July 2018

### Protocol Version [3.0] (12-July-2018)

This amendment is nonsubstantial based on the criteria in Article 10(a) of Directive 2001/20/EC of the European Parliament and the Council of the European Union because it neither significantly impacts the safety or physical/mental integrity of participants nor the scientific value of the study.

After receiving feedback from multiple regulatory agencies, the Sponsor has decided not to initiate the Open-label Extension (OLE) Period.

Section # and Name	Description of Change	Brief Rationale
Throughout	All mention of OLE and related procedures, objectives, and duration estimates were removed	Implementing Sponsor decision to not initiate the OLE Period
Synopsis	Removed Table 2 and Table 3	No longer required given Sponsor decision to not initiate the OLE Period
8.6. Planned Analysis	Removed 12-week analysis and moved consistency analysis to be part of the final analysis	Without the OLE, there is no need to run an interim analysis before the final analysis
Synopsis	Added text to explain removal of OLE Period and provide procedure for subjects already in the OLE Period	Give guidance for subjects who enroll in the OLE Period prior to implementation of Protocol Version 3.0.
7.1.3. Open-label Extension Period	Added text to explain removal of OLE Period and provide procedure for subjects already in the OLE Period	Give guidance for subjects who enroll in the OLE Period prior to implementation of Protocol version 3.0.

This document is the property of Merck KGaA, Darmstadt, Germany, or one of its subsidiaries. It is intended for restricted use only and may not – in full or part – be passed on, reproduced, published or used without express permission of Merck KGaA, Darmstadt, Germany, or its subsidiary. Copyright © 2018 by Merck KGaA, Darmstadt, Germany, or its subsidiary. All rights reserved.

---

## List of Abbreviations

ACR	American College of Rheumatology
ACR20	American College of Rheumatology 20% Response Criteria
ACR50	American College of Rheumatology 50% Response Criteria
ACR70	American College of Rheumatology 70% Response Criteria
AE	Adverse event
ALT	Alanine aminotransferase
APRIL	A proliferation-inducing ligand
AST	Aspartate aminotransferase
AUC	Area under the curve
β-hCG	Beta-human chorionic gonadotropin
bDMARD	Biologic disease-modifying anti-rheumatic drugs
bDMARD-IR	RA subjects with inadequate response to methotrexate and $\geq 1$ bDMARD
BID	Twice daily
BlyS	B lymphocyte stimulator (also called B-cell activating factor or BAFF)
BTK	Bruton's tyrosine kinase
C	Collect
CARLOS	Cartilage Loss Scale
CAT	Computer adaptive testing
CCP	Cyclic citrullinated protein
CDAI	Clinical Disease Activity Index
CI	Confidence interval
C max	Maximum plasma concentration
CRO	Contract research organization
CRP	C-reactive protein
CTCAE	Common Terminology Criteria for Adverse Events
CTR	Clinical trial report
CXR	Chest X-ray
CYP	Cytochrome P450
CYP3A	Cytochrome P450 isozyme 3A
CYP3A4/5	Cytochrome P450 isozyme 3A4/5

DAS	Disease Activity Score
DAS28	Disease Activity Score Based on a 28 Joint Count
DMARD	Disease-modifying anti-rheumatic drugs
DNA	Deoxyribonucleic acid
ECG	Electrocardiogram
eCRF	Electronic Case Report Form
eGFR	Estimated glomerular filtration rate
EMA	European Medicines Agency
ESR	Erythrocyte sedimentation rate
EU	European Union
EULAR	European League Against Rheumatism
FACIT	Functional Assessment of Chronic Illness Therapy
FDA	Food and Drug Administration
FSH	Follicle-stimulating hormone
GCP	Good Clinical Practice
GGT	$\gamma$ -Glutamyl-transferase
HAQ-DI	Health Assessment Questionnaire – Disability Index
HBsAg	Hepatitis B surface antigen
HBV	Hepatitis B Virus
HCV	Hepatitis C Virus
HDL-C	High-density lipoprotein cholesterol
HIV	Human Immunodeficiency Virus
HRQoL	Health-related quality of life
CCI	[REDACTED]
hsCRP	High-sensitivity C-reactive protein
ICF	Informed Consent Form
ICH	International Council for Harmonisation
IDMC	Independent Data Monitoring Committee
IEC	Independent Ethics Committee
Ig	Immunoglobulin
IL	Interleukin
IMP	Investigational Medicinal Product

IRB	Institutional Review Board
ITT	Intent-to-treat
IWRS	Interactive Web Response System
JAK	Janus kinase
JSN	Joint space narrowing
LDA	Low disease activity
LDL-C	Low-density lipoprotein cholesterol
LFT	Liver Function Test
LLN	Lower limit of normal
LTBI	Latent tuberculosis infection
MAR	Missing at random
MCP	Metacarpophalangeal
MedDRA	Medical Dictionary for Regulatory Activities
mITT	Modified Intent-to-Treat
MOP	Manual of Procedures
MRI	Magnetic resonance imaging
mRNA	Messenger Ribonucleic Acid
MTX	Methotrexate
MTX-IR	RA subjects with inadequate response to methotrexate
NIH	National Institute of Health
NSAID	Nonsteroidal anti-inflammatory drug
OLE	Open-label extension
OMERACT	Outcome Measures in Rheumatology Clinical Trials
PCR	Polymerase chain reaction
PD	Pharmacodynamics
CCI	[REDACTED]
PK	Pharmacokinetics
PO	Orally
PP	Per-Protocol
CCI	[REDACTED]
Q2W	Every 14 days
QD	Once daily

R	Review
RA	Rheumatoid arthritis
RAMRIQ	Rheumatoid Arthritis Magnetic Resonance Image Quantification
RAMRIS	Rheumatoid Arthritis Magnetic Resonance Imaging Scoring System
RF	Rheumatoid factor
RNA	Ribonucleic acid
SAE	Serious adverse event
SAP	Statistical Analysis Plan
SDAI	Simplified Disease Activity Index
SF-36	Medical Outcomes Study 36-Item Short Form Health Survey
SJC	Swollen joint count
SLE	Systemic lupus erythematosus
SUSAR	Suspected unexpected serious adverse reaction
TB	Tuberculosis
TJC	Tender joint count
TNF	Tumor necrosis factor
tsDMARD	Targeted synthetic disease-modifying anti-rheumatic drugs
ULN	Upper limit of normal
VAS	Visual analog scale
WOCBP	Women of childbearing potential

1 **Synopsis**

Clinical Trial Protocol Number	MS200527-0060
Title	A Phase IIb, Randomized, Double-blind Study in Subjects with Rheumatoid Arthritis Evaluating the Safety and Efficacy of Evobrutinib Compared with Placebo in Subjects with an Inadequate Response to Methotrexate
Trial Phase	IIb
IND Number	CCI
FDA covered trial	Yes
EudraCT Number	2017-000384-32
Coordinating Investigator	PPD [Redacted] Telephone: PPD E-mail: PPD
Sponsor	For all countries except the USA and Japan: Merck KGaA, [name]  For Japan only: Merck Serono Co., Ltd. (Affiliate of Merck KGaA, Darmstadt, Germany) [name]  And  For the USA: EMD Serono Research & Development Institute, Inc. [name]  Medical Responsible: PPD EMD Serono Research & Development Institute [name] Telephone: PPD

Trial centers/countries	Approximately 160 sites in 17 countries
Planned trial period (first subject in-last subject out)	June 2017 to June 2020
Trial Registry	ClinicalTrials.gov, EudraCT

Objectives:
 
Primary objective:
 
 
To evaluate the efficacy and dose response of 12 weeks of treatment with evobrutinib compared with placebo in subjects with rheumatoid arthritis (RA) with inadequate response to methotrexate (MTX-IR) on stable MTX therapy by assessment of the signs and symptoms of RA, as measured by American College of Rheumatology (ACR) 20% (ACR20) response assessed using high-sensitivity C-reactive protein (hsCRP) at Week 12.
 
 
Key secondary objectives:
 
 
To further evaluate the efficacy and dose response of 12 weeks of treatment with evobrutinib in MTX-IR subjects with RA on stable MTX therapy by assessment of the signs and symptoms of RA, as measured by DAS28-hsCRP low disease activity (DAS28 < 3.2) rate at Week 12
 
To further evaluate the efficacy of 12 weeks of treatment with evobrutinib compared to placebo in MTX-IR subjects with RA on stable MTX therapy by assessment of the signs and symptoms of RA, as measured by DAS28-hsCRP remission (DAS28 < 2.6) rate at Week 12
 
To further evaluate the efficacy and dose response of 12 weeks of treatment with evobrutinib in MTX-IR subjects with RA on stable MTX therapy by assessment of the signs and symptoms of RA, as measured by ACR50 and ACR70 at Week 12
 
To evaluate the safety of evobrutinib in MTX-IR subjects with RA on stable MTX therapy.
 
 
Other secondary objectives:
 
 
To further evaluate the efficacy of evobrutinib on the signs and symptoms of RA with inadequate response to MTX
 
To evaluate the effect of evobrutinib on joint structures and inflammation, at Weeks 4 and 12 in the MRI substudy, as assessed by magnetic resonance imaging (MRI)
 
To evaluate the effect of evobrutinib on physical function in RA subjects
 
To evaluate the effect of evobrutinib on subject-reported health-related quality of life (HRQoL)
 
To evaluate the effect of evobrutinib on subject-reported fatigue (using Functional Assessment of Chronic Illness Therapy [FACIT]-Fatigue).
 
 
Exploratory objectives:
 
CCI [REDACTED]
	

CCI

**Methodology:**

This is a Phase IIb, multicenter, international, randomized, double-blind, placebo-controlled parallel-arm trial, designed to determine the efficacy, dose response, and safety of evobrutinib (also known as M2951) in subjects 18 to 75 years of age with moderate to severe RA, and to consider a dose to take forward into Phase III development.

Enrollment will include approximately 360 MTX-IR subjects with no prior treatment with biologic disease-modifying anti-rheumatic drugs (bDMARD) or targeted synthetic DMARD (tsDMARD).

Approximately 50% of the subjects will participate in a substudy using MRI to evaluate the ability of evobrutinib to prevent the progression of joint structural damage.

Eligible subjects will be randomly assigned in a 1:1:1:1 ratio to receive, in combination with their stable background MTX therapy, evobrutinib 25 mg once daily, evobrutinib 75 mg once daily, evobrutinib 50 mg twice daily, or placebo.

Randomization will be stratified by whether or not subjects are in the MRI substudy and by region.

The trial is composed of a Screening Period of 4 weeks, a Treatment Period of 12 weeks, and a Safety Follow-up Period of 4 weeks. After completing the 12-week Treatment Period, subjects will enter into safety follow up period.

In Protocol version 2.0, subjects completing the Treatment Period could have entered an optional Open-label Extension (OLE) Period, but the Sponsor made the decision to not initiate the OLE Period. As of the effective date of Protocol version 3.0 at study sites, all subjects completing the Treatment Period will enter the Safety Follow-up Period, and any subjects already participating in the OLE Period at that time will be immediately withdrawn from the study following the protocol-specified withdrawal procedures: subjects would return for an End of Treatment Visit and return 4 weeks later for an End of Study/Safety Follow-up Visit.

During the trial, clinical efficacy endpoints will be evaluated using assessments of clinical response, disease activity and remission, prevention of joint structural damage progression, physical function, fatigue, and HRQoL. Safety will be evaluated through the nature,

occurrence, severity and outcome of adverse events (AEs), and assessment of physical examination findings, electrocardiograms (ECGs), hematology and chemistry laboratory assessments, vital signs, and absolute values and change from Baseline in serum total immunoglobulin (Ig) levels (IgG, IgA, and IgM) and total B cell counts.

**Planned number of subjects:** 360 subjects with RA (to achieve 320 evaluable subjects)

**Primary endpoint:**

Primary efficacy endpoint: ACR20 response assessed using hsCRP (ACR20) at Week 12.

**Key secondary endpoints:**

Key secondary efficacy endpoints:

- DAS28-hsCRP low disease activity (DAS28 < 3.2) rate at Week 12
- DAS28-hsCRP remission (DAS28 < 2.6) rate at Week 12
- ACR 50% (ACR50) response assessed using hsCRP at Week 12
- ACR 70% (ACR70) response assessed using hsCRP at Week 12.

Key secondary safety endpoints:

- The nature, severity, and occurrence of AEs and serious AEs (SAEs)
- Absolute values and change from Baseline in:
  - Vital signs
  - ECG parameters including RR interval, PR interval, QRS duration, QT interval, and QTcF interval
  - Serum Ig levels (IgG, IgA, IgM)
  - Total B cell counts
  - Clinical laboratory parameters.

**Other secondary efficacy endpoints:**

At Week 12:

- Achieving American College of Rheumatology/European League Against Rheumatism (EULAR) Boolean remission
- Achieving Clinical Disease Activity Index (CDAI) score  $\leq$  2.8 (CDAI remission)
- Achieving Simplified Disease Activity Index (SDAI) score  $\leq$  3.3 (SDAI remission)
- EULAR Responder Index (based on DAS-hsCRP)
- ACR hybrid scores computed using hsCRP
- Change from Baseline in DAS28-hsCRP
- Change from Baseline in CDAI and SDAI

- Changes and percentage changes from Baseline of individual components of the ACR Core Set
- Imaging:
  - Change from Baseline in Outcome Measures in Rheumatology Clinical Trials (OMERACT) Rheumatoid Arthritis Magnetic Resonance Imaging Scoring System (RAMRIS) scores (designated hand, minimal assessed joints: wrist, metacarpophalangeal [MCP] joints #1 to #5) for subjects in the MRI substudy:
    - Synovitis score
    - Bone marrow edema (osteitis) score.
- Changes from Baseline of Physical Function:
  - Health Assessment Questionnaire – Disability Index (HAQ-DI).
- Changes from Baseline of HRQoL:
  - Medical Outcomes Study 36-item Short Form Health Survey (SF-36)
  - Functional Assessment of Chronic Illness Therapy (FACIT)-Fatigue.

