### **Lineplot:**

Mean score CFB will be presented as a by-visit line plot for each treatment group, with all treatment groups included in a single figure, and horizontal axis extending to Week 12 (RAMRIS Synovitis and Osteitis only).

#### 14.2.4 HRQoL Endpoints at Week 12

The following HRQoL endpoints will be presented on QoL analysis set:

- HAQ-DI
- SF-36
- FACIT-Fatigue

CCI [Redacted]

HAQ-DI scoring is detailed in Appendix 18.2.

A full description of the scoring rules of each health concept of SF-36 as well as Physical Component Summary (PCS) and Mental Component Summary (MCS) is available in Appendix 18.3.

A full description of the scoring instructions of FACIT-Fatigue scale is available in Appendix 18.4.

CCI [Redacted]

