**Table 18 : Analysis of HRQoL Endpoints at Week 12**

Endpoints	Analysis Set	Analysis method	Missing data handling

 
• HAQ-DI Total Score
 
	
 
• QoL set
 
	
 
• MMRM
 
	As observed

 
• SF-36 (Change in PCS, MCS scores, and their components)
 
• FACIT-Fatigue (Change in Total score over time)
 
 
CCI [Redacted]
	
 
• QoL set
 
	
 
• MMRM model
 
• Descriptive statistics
 
• Probability of achieving %CFB value or higher
 
• Logistic regression
 
	As observed

**MMRM model:** similar as in Section 14.2.3.

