### **Logistic regression:**

Response on the SF-36 (PCS, PF, VT), FACIT-Fatigue total score and CCI will be further analyzed based on differences in proportion of responders, comparing each dose of evobrutinib versus placebo.

Responder definitions will be based on minimal clinically important difference (MCID) criteria for improvement or deterioration as follows:

- SF-36 - PCS:
  - Improvement is defined as an increase greater or equal to 2.5 compared to baseline
  - Deterioration is defined as a decrease greater or equal to 0.8 compared to baseline
- SF-36 – domain scores:
  - Improvement is defined as an increase greater or equal to 5.0 compared to baseline
  - Deterioration is defined as a decrease greater or equal to 2.5 compared to baseline
- FACIT-Fatigue Total Score:
  - Improvement is defined as an increase greater or equal to 4.0 compared to baseline

- Deterioration is defined as a decrease greater or equal to 4.0 compared to baseline

CCI

Logistic regression model for repeated measures will be applied, with adjustments for the region, baseline value and with treatment as a factor. An example of SAS code is available in Appendix 18.5.

### 14.2.5 Exploratory Efficacy Endpoints at Week 12

CCI

CCI

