**Table 32: SF-36 – Abbreviated Item Content for the SF-36v2 Health Domain Scales**

Scale	Original item#	Item# in the MS200527-0060 study	Abbreviated Item Content
Physical Functioning (PF)	3a	3	Vigorous activities, such as running, lifting heavy objects, or participating in strenuous sports
	3b	4	Moderate activities, such as moving a table, pushing a vacuum cleaner, bowling, or playing golf
	3c	5	Lifting or carrying groceries
	3d	6	Climbing several flights of stairs
	3e	7	Climbing one flight of stairs
	3f	8	Bending, kneeling, or stooping
	3g	9	Walking more than a mile
	3h	10	Walking several hundred yards
	3i	11	Walking one hundred yards
	3j	12	Bathing or dressing oneself
Role-Physical (RP)	4a	13	Cut down the amount of time spent on work or other activities
	4b	14	Accomplished less than you would like
	4c	15	Limited in kind of work or other activities
	4d	16	Had difficulty performing work or other activities (eg, it took extra effort)
Bodily Pain (BP)	7	21	Intensity of bodily pain
	8	22	Extent pain interfered with normal work
General Health (GH)	1	1	Is your health: excellent, very good, good, fair, poor
	11a	33	Seem to get sick a little easier than other people
	11b	34	As healthy as anybody I know
	11c	35	Expect my health to get worse
	11d	36	Health is excellent
Vitality (VT)	9a	23	Feel full of life
	9e	27	Have a lot of energy
	9g	29	Feel worn out
	9i	31	Feel tired
Social Functioning (SF)	6	20	Extent health problems interfered with normal social activities
	10	32	Frequency health problems interfered with social activities
Role-Emotional (RE)	5a	17	Cut down the amount of time spent on work or other activities
	5b	18	Accomplished less than you would like
	5c	19	Did work or other activities less carefully than usual
Mental Health (MH)	9b	24	Been very nervous
	9c	25	Felt so down in the dumps that nothing could cheer you up
	9d	26	Felt calm and peaceful
	9f	28	Felt downhearted and depressed
9h	30	Been happy	
Self-Evaluated Transition (SET)	2	2	How health is now compared to 1 year ago

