**Step 2: Determining Health Domain Scale Scores (0-100 Scores)**

After item recoding, a total raw score is computed for each health domain scale. The total raw score is the simple algebraic sum of the final response values for all items in a given scale, as shown in Table 34. The total raw score for each scale is transformed to a 0-100 scale score using the following formula:

$$Total\ raw\ score = 100 \times \frac{(Raw\ score - Lowest\ possible\ raw\ score)}{Possible\ raw\ score\ range}$$

**Table 34: SF-36 – Values used in transforming SF-36v2 Health Survey Health Domain Scale Total Raw Scores on the 0-100 Scale**

Scale	Sum of Final Response Values	Lowest and highest possible total raw scores	Possible total raw score range
PF	3a+3b+3c+3d+3e+3f+3g+3h+3i+3j	10, 30	20
RP	4a+4b+4c+4d	4, 20	16
BP	7+8	2, 12	10
GH	1+11a+11b+11c+11d	5, 25	20
VT	9a+9c+9g+9i	4, 20	16
SF	6+10	2, 10	8
RE	5a+5b+5c	3, 15	12
MH	9b+9c+9d+9f+9h	5, 25	20

Raw and transformed scale scores are not calculated for the Reported Health Transition (HT) item.

As recommended by the developers of the questionnaire, missing item responses will be treated using the “Half-scale rule”, which states that a score can be calculated if the respondent answers at least 50% of the items in a multi-item scale. In such cases, the missing item data will be replaced by the mean of the answered items of its scale. If more than 50% of the items are missing within a scale, the scale score will be missing.

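### SAP Appendix 18.3 contradicts itself on SF-36 scoring: the Vitality item sum needs a page check, and the worked example has a wrong Role-Emotional divisor and a wrong MCS

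*Protocol*

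**What the plan says.** The Protocol synopsis (other secondary efficacy endpoints) includes change from baseline in the "Medical Outcomes Study 36-item Short Form Health Survey (SF-36". SAP Section 14.2.4 sends the reader to Appendix 18.3 for "A full description of the scoring rules of each health concept of SF-36" and of the two summary scores. SAP Table 18 covers "SF-36 (Change in PCS, MCS scores, and their components", analysed by MMRM, descriptive statistics, cumulative curves and logistic regression. The logistic regression text singles out three SF-36 scores: "Response on the SF-36 (PCS, PF, VT), FACIT-Fatigue total score".

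Within Appendix 18.3:

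- **Table 32** puts items 9a, 9e, 9g and 9i in Vitality. Item 9e is "Have a lot of energy". Item 9c, "Felt so down in the dumps that nothing could cheer you up", is in Mental Health.
- **Table 34**, as it reads, sums Vitality as 9a + 9c + 9g + 9i, and also uses 9c in the Mental Health sum. It gives Role-Emotional a lowest score of 3, a highest of 15 and a range of 12.
- **Step 2** states: "The total raw score for each scale is transformed to a 0-100 scale score using the following formula", namely 100 × (raw − lowest possible) / possible range.
- **Table 38** (worked example) shows a Vitality raw score of 11. It shows Role-Emotional as 100 × (7−3)/15 = 27, z = -2.82, normalized 21.8. Below the table the example gives PCS = -0.41 (45.9) and MCS = -2.62 (23.8).

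**The concern.** There are two separate problems.

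(a) If Table 34 really reads 9c, a scoring rule is wrong. Item 9c would count in two scales and 9e in none. Code that follows the table would mis-score Vitality, which enters the MMRM and the responder analysis. Through Vitality it would also shift PCS and MCS slightly.

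(b) The worked example is the appendix's only numerical run from raw answers to PCS and MCS. It does not follow from the tables it illustrates. Correct code would disagree with it on Role-Emotional, PCS and MCS, so it cannot serve as a check of the SF-36 derivation.

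**Working it through.** **Inputs.** Answers from Table 37, recoding from Table 33, item sums and ranges from Table 34, means and SDs from Table 35, coefficients from Table 36. The steps are: z = (0–100 score − mean)/SD; normalized domain score = 50 + 10z; PCS or MCS = sum of z × coefficient; normalized summary = 50 + 10 × that sum.

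**Raw scores.** With the items of Table 32, all eight raw scores in Table 38 reproduce: PF 19, RP 10, BP 8.2, GH 19, VT 11, SF 8, RE 7, MH 12.

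**Vitality.** The example answers are 9a = 4 (recoded 2), 9e = 3 (recoded 3), 9g = 4 and 9i = 2 (both as recorded), and 9c = 2 (as recorded).

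- With 9e: 2 + 3 + 4 + 2 = 11; 100 × (11−4)/16 = 43.75; z = (43.75 − 58.31411)/20.01923 = -0.73; normalized 42.7. This is the SAP's figure.
- With 9c: 2 + 2 + 4 + 2 = 10; 100 × (10−4)/16 = 37.5; z = -1.04; normalized 39.6.

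One raw Vitality point is 100/16 = 6.25 on the 0–100 scale, or 10 × 6.25/20.01923 = 3.1 normalized points. Carried into the summary scores, it moves MCS by 3.1 × 0.23534 = 0.7 points and PCS by 3.1 × 0.028877 = 0.1 points.

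**Role-Emotional.** The stated 27 is 100 × 4/15 = 26.7 rounded, and the stated z and normalized score follow from 27. So 15 was used in the calculation and is not a misread digit. With the Table 34 range: 100 × (7−3)/12 = 33.3; z = (33.3 − 87.39733)/21.43778 = -2.52; normalized 24.8.

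**PCS and MCS from the SAP's own printed z-scores:**

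| Scale | z | z × PCS coefficient | z × MCS coefficient |
|---|---|---|---|
| PF | -1.61 | -0.683 | +0.370 |
| RP | -1.76 | -0.618 | +0.217 |
| BP | -0.39 | -0.124 | +0.038 |
| GH | -0.04 | -0.010 | +0.001 |
| VT | -0.73 | -0.021 | -0.172 |
| SF | -0.41 | +0.003 | -0.110 |
| RE | -2.82 | +0.542 | -1.224 |
| MH | -2.25 | +0.497 | -1.093 |
| Sum | | -0.414 | -1.973 |

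PCS = -0.41, normalized 45.9, matches the SAP, which confirms the z-scores and the method. MCS = -1.97, normalized 30.3, does not match the stated -2.62 (23.8). Dropping or sign-flipping any single term does not give -2.62; matches need two or more such changes.

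**With Role-Emotional corrected (z = -2.52).** MCS changes by 0.30 × 0.43407 = +0.13 to -1.84, normalized 31.6. PCS changes by 0.30 × (-0.19206) = -0.06 to -0.47, normalized 45.3. The stated MCS is therefore 30.3 − 23.8 = 6.5 points below what its own inputs give, and 31.6 − 23.8 = 7.8 points below the corrected value.

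**The case against.** The only discrepancy that touches a scoring rule rests on one letter, and c and e are easily confused in machine-read PDF text. Table 32 and the example both point to 9e. This stands: the Vitality row is a query until the page has been looked at.

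The Role-Emotional and MCS errors lie in an illustration. The formula, the range of 12 and the coefficients in Tables 34 to 36 are not in conflict with one another, and the appendix also cites the instrument's user manual. Code built from Tables 33 to 36 scores Role-Emotional and weights MCS correctly. Nothing in the documents says that the program will be validated against the example. This also stands, and it confines problem (b) to a misleading check.

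The appendix partly exposes its own slips, since code using 9c would fail the example at the Vitality raw score. That is true, but correct code would fail it too, on Role-Emotional, PCS and MCS, so the example cannot tell right from wrong code.

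The stakes are limited. SAP Section 14.2 calls the secondary analyses supportive, with nominal p-values, and Protocol Section 8.5.3.4 plans only descriptive summaries for SF-36.

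**Conclusion.** The appendix contradicts itself and should be corrected; the severity is minor. The Role-Emotional divisor and the MCS value are certain errors in the example, with a knock-on to its PCS (45.9 should be 45.3). The Vitality sum is wrong as it reads, on the assumption that the page does say 9c. In that case Vitality would be mis-scored in the MMRM and the responder analysis, with small effects on PCS and MCS. ACR20, the key secondary endpoints and the multiplicity procedure are unaffected.

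A reader might infer more, but the documents do not support it:

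- That the trial's Role-Emotional and MCS results will be wrong. This would require a programmer to override Table 34 or Table 36.
- That the 3.1-point Vitality gap or the MCS gaps can be judged against the responder and worsening thresholds in Section 14.2.4. Those thresholds apply to change from baseline within a subject. The gaps are differences in level for one example respondent at one time, and the same code would run at both visits.
- That the Vitality treatment effect would be diluted by a known percentage. This needs an assumed effect on item 9c, which the documents do not give.

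**What to change.** 1. Look at the Vitality row of Table 34 on the SAP page. If it reads 9c, correct the sum to 9a + 9e + 9g + 9i. If it reads 9e, no change is needed there.
2. In Table 38, correct Role-Emotional to 100 × (7−3)/12 = 33.3, z = -2.52, normalized 24.8.
3. Restate the example's summary scores as PCS = -0.47 (45.3) and MCS = -1.84 (31.6).
4. Re-check the SF-36 derivation program against the corrected tables and example before unblinding.

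The cost is a few cells in a SAP appendix and one repeat of the derivation check. No data collection, sample size or analysis model changes.
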